#### **6.4.2. Re-Screening Criteria**

Subjects who do not enroll within 28 days of screening will be screen failed.

Re-screening may be allowed. Subjects who are re-screened will be re-consented with new screening number, and will repeat the screening assessments. Gilead is to be informed prior to a subject re-screening.

#### **6.5. Treatment Assessments**

Each on-study visit will be scheduled relative to C1D1. Visits will follow the schedule of assessments in [Appendix 2](#) and [Appendix 3](#).

### **6.5.1. Study Day 1**

Only subjects enrolled into a combination therapy and who have met all eligibility criteria will return to the clinic on Study Day 1 to perform baseline assessments.

The following baseline assessments will be conducted prior to the first dose of enzalutamide:

- Physical examination, including weight
- Vital signs, within 15 minutes prior to the enzalutamide dose
- ECOG performance status
- Laboratory assessments and blood sampling (refer to [Table 6-1](#))
  - Chemistry
  - CBC with differential
  - Urinalysis
  - Coagulation
- Record any adverse events
- Concomitant medications review
- IP accountability and dispensing of Enzalutamide and Dosing Diary.

### **6.5.2. Baseline Visit / Cycle 1 Day 1 (C1D1)**

Subjects in a monotherapy treatment who have met all eligibility criteria will return to the clinic on C1D1 to perform baseline assessments. C1D1 is defined as the date of the first dose of GS-5829, and may occur within 3 days following enrollment.

The following baseline assessments will be conducted prior to the first dose of GS-5829:

- Physical examination, including weight
- Vital signs, within 15 minutes prior to the GS-5829 dose
- Triplicate 12-lead ECG
- ECOG performance status

- Laboratory assessments and blood sampling (refer to [Table 6-1](#))
  - Chemistry
  - CBC with differential
  - Coagulation
  - Request archival tumor tissue specimen: Efforts to acquire tissue sample should begin on C1D1 for all subjects
  - Urinalysis
  - GS-5829 PK (see [Appendix 2](#) and [Appendix 3](#))
  - Pharmacodynamics (see [Appendix 2](#) and [Appendix 3](#))
  - PSA
- Record any adverse events
- Concomitant medications review
- IP accountability and dispensing of IP and Dosing Diary.

The site will train the subject on the dosing schedule for the IP and the Dosing Diary at the time of dispensing.

The following assessments will be conducted after the first dose of GS-5829:

- Triplicate ECG (see [Appendix 2](#) and [Appendix 3](#))
- Vital signs (2 and 4 hours post GS-5829 dose [ $\pm 15$  minutes])
- GS-5829 PK (see [Appendix 2](#) and [Appendix 3](#))
- Pharmacodynamics (see [Appendix 2](#) and [Appendix 3](#))

#### **6.5.3. Cycle 1 Day 8, Day 15 and Day 22 (C1D8, C1D15, and C1D22)**

The following assessments will be conducted:

- Physical exam, including weight
- Vital signs

- ECOG Performance Status (Days 8 and 22 only)
- Laboratory assessments and blood sampling (refer to [Table 6-1](#), [Appendix 2](#) and [Appendix 3](#))
  - Chemistry
  - CBC with differential
  - Coagulation (D8 only)
  - GS-5829 PK (see [Appendix 2](#) and [Appendix 3](#))
  - Pharmacodynamics (C1D8 and C1D15)
  - Urinalysis (C1D8 only)
- Triplicate 12-lead ECG (see [Appendix 2](#) and [Appendix 3](#))
- Record any adverse events
- Concomitant medications review

#### **6.5.4. Cycle 2 Day 1 (C2D1) and Day 1 of Subsequent Cycles**

On-study visits during the treatment period may be completed within a window of  $\pm$  7 days. The following procedures will be completed on Day 1 of each subsequent cycle:

- Physical examination, including weight
- Vital signs
- Triplicate 12-lead ECG
- ECOG Performance Status
- Laboratory assessments and blood sampling (refer to [Table 6-1](#))
  - Chemistry
  - CBC with differential
  - GS-5829 PK (see [Appendix 2](#) and [Appendix 3](#))
  - Pharmacodynamics (see [Appendix 2](#) and [Appendix 3](#))
  - Urinalysis
  - PSA

CCI

- Record any adverse events
- Concomitant medications review
- IP accountability and dispensing of IP and Dosing Diary

#### **6.5.5. End of Treatment (EOT) Visit**

The following procedures will be conducted when a subject discontinues GS-5829, with a window of  $\pm$  7 days, and prior to initiating a new anti-cancer regimen:

- Complete Physical examination, including weight
- Vital signs (pre-dose only)
- Triplicate 12-lead ECG
- ECOG performance status
- Laboratory assessments and blood sampling
  - Chemistry
  - CBC with differential
  - Coagulation
  - Urinalysis
  - PSA
- **cci** [REDACTED]
- Bone scan (not necessary if restaging scan was performed within the prior 4 weeks)
- CT with contrast or MRI (not necessary if restaging scan was performed within the prior 4 weeks)
- Record any adverse events
- Concomitant medications review
- IP/Dosing Diary accountability

## **6.6. Post-Treatment 30-Day Safety Follow-up Visit**

All subjects will complete the 30-Day Safety Follow-Up visit. For Phase 1b Dose Escalation subjects, the 30-Day Safety Follow-Up will be the final study visit. Phase 2 Dose Expansion subjects will complete the 30-Day Safety Follow-Up Visit and proceed to Long Term Survival Follow-Up.

The following procedures will be completed 30 days after the subject's last dose of IP, within a window of  $\pm$  7 days:

- Physical examination, including weight
- Vital signs
- ECOG performance status
- Laboratory assessments
  - Chemistry
  - CBC with differential
  - Urinalysis
- Concomitant medications review
- Record any adverse events (30 days post last dose of IP)

For subjects who come off study treatment for reasons other than disease progression, the Investigator should also obtain information on the subject's post-study anti-cancer therapies, surgeries, and date of definitive disease progression (if known).

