### 3.3. Study Treatments

Subjects who meet eligibility criteria will receive GS-5829 as a single agent or combined with enzalutamide orally once daily. Each cycle will consist of 28 days. Safety and efficacy assessments will occur on an outpatient basis including assessment of tumor response, physical exam, vitals, electrocardiogram (ECG), collection of blood samples (for routine safety labs, GS-5829 PK, PD markers, and biomarkers at applicable visits), and assessment of AEs. In addition, subjects will undergo a bone scan and CT (or MRI) every 12 weeks.

A subject who does not show evidence of disease progression may continue receiving GS-5829 as a single agent or combined with enzalutamide once daily until disease progression (clinical or radiographic), unacceptable toxicity, withdrawal of consent, or other reasons specified in Section 3.4. Subjects who have progressive disease by PSA measurements alone may continue study drug.

Following treatment, subjects will be followed for safety for 30 days and for survival.

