### 3.4. Criteria for Discontinuation of Study Drug

Study medication may be discontinued in the following instances:

- Documented progression of malignant disease
- Death
- Investigator discretion
- Non-compliance with study drug
- Important protocol deviation

- Subject decision
- Lost to follow-up
- Study termination by the sponsor
- Intercurrent illness that would, in the judgment of the investigator, affect assessments of clinical status to a significant degree
- Unacceptable toxicity, as defined in the toxicity management section of the protocol, or toxicity that, in the judgment of the investigator, compromises the ability to continue study-specific procedures or is considered to not be in the subject's best interest

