## **6.7. Long Term Survival Follow-Up**

Phase 2 Dose Expansion subjects will participate in long term survival follow-up. These subjects will be contacted via phone call every 3 months for determination of long term survival status and record of any other anti-cancer therapy for up to 2 years after the last dose of IP. For subjects who discontinued the study for reasons other than disease progression, the Investigator should obtain information on the subject's post-study anti-cancer therapies, surgeries, and date of definitive disease progression (if known).

Subjects who are alive at the time the sponsor has made the determination the study will be ended will receive a final follow-up phone call to assess survival status and communicate the sponsor's decision. These subjects will be censored on the date the subject was last contacted.

The investigator will make every effort to contact the subject or a close relative or caretaker by phone to collect survival information. The investigator should show due diligence by documenting in the source documents steps taken to contact the subject i.e., dates of phone calls, registered letters, etc.

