6. EFFICACY ANALYSES

6.1. Primary Efficacy Endpoint

6.1.1. Definition of the Primary Efficacy Endpoint

The primary efficacy endpoint of this study is non-progression rate at Week 24 defined as the proportion of subjects who don't progress by Week 24. The progression is determined by the investigators based on Prostate Cancer Working Group 2 (PCWG2) Criteria for lesion scans, bone scans and PSA assessments together. Subjects will be considered as having definitive disease progression if any of three progression criteria meets. Progression-free survival (PFS), defined as the interval from start of study drug to the earlier of the first documentation of definitive disease progression or death from any cause. Definitive disease progression is determined by investigator based on PCWG2 criteria.

The date of definitive progression will be the time point at which progression is first identified. The death from any cause to be considered as PFS event should occur within the time window of 2 consecutive scheduled tumor assessments after the last tumor assessment. Non-evaluable (NE) and no disease (ND) are considered as not adequate.

Subjects will be censored on the date of Study Day 1 if

- no adequate baseline target lesion assessment nor bone scan is available (note: baseline PSA assessment missing is allowed) and subject didn't die before or on the 2nd scheduled post-baseline tumor assessment without receiving anti-cancer therapy;
- or if no adequate post-baseline tumor assessment is available and subjects didn't die
- or if no adequate post-baseline tumor assessment is available and subjects died after the 2nd scheduled tumor assessment.

Subjects will be censored on the date of last adequate post-baseline tumor assessment, or Day 1 if the last post-baseline adequate tumor assessment doesn't exist, for the following situations:

- who do not have documented progression or die, or
- who start new anticancer therapy before documented progression, or
- who start new anticancer therapy before death without documented progression, or
- who have ≥ 2 consecutive missing post-baseline tumor assessments immediately before documented progression, or
- who have ≥ 2 consecutive missing post-baseline tumor assessments immediately before death without documented progression

Table 6-1 below provides detailed event/censoring scheme for PFS derivation and the derivation diagram provides all decisions on event/censoring indicators and time.

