Table 6-1. Event/Censoring Scheme of Analysis for PFS

PFS Derivation Step	Situation	Date of Progression or Censoring	Outcome
1	No adequate baseline tumor assessments and subjects didn't die before or on the 2nd scheduled post-baseline tumor assessment	Study Day 1	Censored
1	No adequate baseline tumor assessments and subjects died before or on the 2nd scheduled post-baseline tumor assessment without receiving anti-cancer therapy	Date of death	Event
1	No adequate baseline tumor assessments, subjects died before or on the 2nd scheduled post-baseline tumor assessment and received anti-cancer therapy	Study Day 1	Censored
2	No adequate post-baseline tumor assessments and subjects did not die	Study Day 1	Censored
2	No adequate post-baseline tumor assessments and subjects died after the 2nd scheduled post-baseline tumor assessment	Study Day 1	Censored
2	No adequate post-baseline tumor assessments and subjects died before or on the 2nd scheduled post-baseline tumor assessment without receiving anti-cancer therapy	Date of death	Event
2	No adequate post-baseline tumor assessments, subjects died before the 2nd scheduled post-baseline tumor assessment and received anti-cancer therapy	Study Day 1	Censored
3	Documented progression and didn't receive anti-cancer therapy or have ≥ 2 consecutive missing post-baseline tumor assessments immediately before documented progression	Date of the first documented progression	Event
3	Death without progression and within the time window of 2 consecutive scheduled post-baseline tumor assessments after the last tumor assessment and didn't receive anti-cancer therapy or have ≥ 2	Date of death	Event

PFS Derivation Step	Situation	Date of Progression or Censoring	Outcome
	consecutive missing post-baseline tumor assessments immediately before death		
3	No documented progression or death and didn't receive anti-cancer therapy or have ≥ 2 consecutive missing post-baseline tumor assessments	Date of the last adequate post-baseline tumor assessment	Censored
4	Start new anticancer therapy without or before documented progression or death or have ≥ 2 consecutive missing post-baseline tumor assessments immediately before documented progression or death	The later one of 1) Date of the last adequate post-baseline tumor assessment on/prior to the new anticancer therapy start date and/or the consecutive missing 2) Study Day 1	Censored

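### A subject taken off drug for clinical progression with no PCWG2 event is censored for PFS, which pushes the Kaplan-Meier rates upward, and the SAP has no sensitivity analysis to show by how much

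*Protocol*

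**What the plan says.** **Stopping drug.** Protocol Section 3.3 and the synopsis continue treatment "until disease progression (clinical or radiographic), unacceptable toxicity, withdrawal of consent" or another reason in Section 3.4. Section 3.4 words the corresponding reason as "Documented progression of malignant disease" and has no separate line for clinical progression.

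**Counting a PFS event.** SAP Section 6.1.1 bases progression on "Prostate Cancer Working Group 2 (PCWG2) Criteria for lesion scans, bone scans and PSA assessments together" and adds: "Subjects will be considered as having definitive disease progression if any of three progression criteria meets". Clinical progression is not one of the three. A death counts only inside the window of two scheduled assessments and without new anticancer therapy.

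**Censoring.** In Table 6-1, a subject with neither documented progression nor death is censored at the "Date of the last adequate post-baseline tumor assessment", or at Study Day 1 if there is none. New anticancer therapy before documented progression also leads to censoring, so a later progression or death is not counted.

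**Collecting a later date.** Protocol Section 6.6 states: "For subjects who come off study treatment for reasons other than disease progression, the Investigator should also obtain information on" later anticancer therapy, surgery and the date of definitive progression, if known. Section 6.7, which covers Phase 2 only, has a parallel sentence: "For subjects who discontinued the study for reasons other than disease progression, the Investigator should obtain information" of the same kind.

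**Analysis.** SAP Section 6.1.2 gives Kaplan-Meier estimates of PFS with rates at 24 and 48 weeks, and a simple count at Week 24. It has no sensitivity analysis for clinical progression and does not say how such subjects enter the count.

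**The concern.** The same subject can be progressed for conduct and not progressed for analysis. Kaplan-Meier treats a censored subject as having the same outlook as those still at risk. A subject whose drug was stopped because the investigator judged the disease to be progressing does not have that outlook. Each such censoring lifts the curve, and in an uncontrolled study no comparator carries the same bias. If the later progression date is also not sought from these subjects, nothing in the data would show how much of the reported PFS depends on the rule.

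**Working it through.** **1. The plan's own figure.** Protocol Section 8.9 says that more than 10 non-progressors among 20 gives a lower 90% bound above 30%. Section 8.3 specifies exact two-sided intervals. The Clopper-Pearson lower limit is the 5% quantile of Beta(x, n − x + 1).

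- 11/20: 34.7% to 74.1%
- 10/20: 30.2% to 69.8%

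The statement reproduces. For comparison, the lower limits for 9/20 and 8/20 are 25.9% and 21.7%.

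**2. How a subject reaches censoring.** The investigator stops drug on clinical grounds. Protocol Section 6.5.5 then requires PSA, bone scan and CT or MRI, but waives the scans if restaging was done in the prior 4 weeks. Under Appendix 5, new bone lesions at the first reassessment need a confirmatory scan at least 6 weeks later, and PSA progression without a prior decline counts only after 12 weeks. An early clinical progressor can therefore miss all three criteria. If he then starts new therapy, Table 6-1 censors him whatever follows.

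**3. Size, simple model.** Let S be the Week-24 rate when clinical progression counts as progression. Let c be the share of the progression hazard that is clinical only. The documents do not give c, so it is assumed. If all of that share is censored, Kaplan-Meier estimates S^(1−c).

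| c | S = 30% | S = 40% |
|---|---|---|
| 10% | 0.30^0.9 = 33.8% | 0.40^0.9 = 43.8% |
| 20% | 0.30^0.8 = 38.2% | 0.40^0.8 = 48.0% |
| 30% | 0.30^0.7 = 43.1% | 0.40^0.7 = 52.7% |

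**4. Size, with the SAP's censoring date.** The model in step 3 censors at the moment of progression. The SAP censors at the last adequate assessment, and scans are 12 weeks apart. With a constant hazard, let q be the chance of no progression over 12 weeks, so S = q². In each interval the fraction c(1 − q) leaves the risk set at its start and (1 − c)(1 − q) are events at its end. The interval estimate is q / [1 − c(1 − q)], and the Week-24 estimate is its square.

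- S = 30%, q = 0.5477: 32.9%, 36.3% and 40.2% at c = 10%, 20% and 30%.
- Median 15 weeks (the background figure in Section 8.9 for enzalutamide failures given abiraterone), q = 2^(−12/15) = 0.574, true rate 33%: 36%, 39%, 43% and 48% at c = 10%, 20%, 30% and 40%.

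**5. Size, in 20 subjects.** Suppose 7 progress by Week 12, 7 more by Week 24, and 6 do not (true rate 30%). Let k of the 14 progressors be clinical only.

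| k (share of 14) | Censored at Week 12: (13/20) × 6/(13 − k) | Censored at Day 1: 6/(20 − k) |
|---|---|---|
| 1 (7%) | 32.5% | 31.6% |
| 2 (14%) | 35.5% | 33.3% |
| 4 (29%) | 43.3% | 37.5% |
| 6 (43%) | 55.7% | 42.9% |

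**6. The simple count.** In the same example the count is 6/20 (lower 90% limit 14.0%) if these subjects are classed as progressed, and (6 + k)/20 if not. With k = 5, five of the 14 progressors, the second reading gives 11/20 and a lower limit of 34.7%. The SAP does not say which reading applies.

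Steps 3 to 5 assume that no end-of-treatment test, earlier PSA rise, later scan or qualifying death turns any of these subjects into an event.

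**The case against.** **Many clinical progressors will still be events.** PSA is measured every cycle, and PSA progression is a SAP event even though it need not stop drug. PSA, bone scan and CT or MRI fall due at end of treatment, before any new regimen. Unscheduled scans are allowed, and some deaths qualify. This stands. A reader might infer that Kaplan-Meier censors everyone stopped for clinical progression. It censors only those negative on all of these.

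**Exclusion from later collection is not established.** Section 3.4 speaks of documented progression, and Sections 6.6 and 6.7 ask for the date of definitive progression, which Protocol Section 8.1.3 ties to PCWG2. A stop without PCWG2 progression could therefore count as a reason other than progression, and the date would be requested. The wording of Section 3.3 points the other way. This is an unreconciled term, not a proven exclusion.

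**These subjects are not lost from view.** A reader might infer that follow-up ends and that any later information consists of events only. All subjects have the 30-day visit, Phase 2 subjects have 3-monthly calls, and Section 6.10 asks for 12-weekly scans until progression or new therapy. Those scans can also show no progression.

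**A true 30% would not read as clearly above 30%.** The highest value in step 3 for a true 30% is 43.1%, or 8.6 of 20. Even 9/20 has a lower 90% limit of 25.9%.

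**A PCWG2-only event is a defensible choice** in an open-label study, and it follows the protocol's PFS definition. This also stands. It does not make the censoring non-informative: a subject stopped for clinical deterioration is likely to be closer than average to PCWG2 progression.

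**Reach is limited.** SAP Section 1 says that Phase 2 did not open and that all Phase 1b subjects have stopped drug and had the safety follow-up visit. Section 6.7 never applied, and rewording Section 6.6 recovers little now.

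**Conclusion.** The point holds for subjects stopped on clinical grounds who have no PCWG2 progression and no qualifying death. Their censoring is informative, its direction favours the drug, and the SAP has no analysis that would reveal its effect. The size cannot be derived from the documents, because it turns on the share of clinical-only progression. For an assumed share of 10% to 30%, a true 30% at Week 24 would read as about 34% to 43%. This is an upper case, since it lets no other test or event catch these subjects; censoring at the last scheduled scan under a constant hazard gives 33% to 40%. What is affected in practice is descriptive PFS in Phase 1b cohorts of 3 to 6 subjects, with no formal testing, so the matter is one of transparent reporting. The follow-up wording is a secondary point and rests on an ambiguous term.

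**What to change.** **In the SAP, before database finalization.**

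- In Section 6.1.2 add a sensitivity Kaplan-Meier analysis of PFS and the Week-24 rate. Count discontinuation for disease progression without a PCWG2 event as an event on the discontinuation date, and report it beside the main estimate.
- State how these subjects are classed in the Week-24 count.
- Identify them as stopped for progression with no PCWG2 event. The recorded discontinuation reason may not separate clinical from documented progression, since Protocol Section 3.4 has no such category. SAP Section 4.1 already summarizes discontinuation reasons.

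**In any amendment or successor protocol.** Reconcile the term disease progression across Sections 3.3, 3.4, 6.6, 6.7 and 6.10. Have Sections 6.6 and 6.7 request the progression date for every subject who stops without PCWG2-documented progression.

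**Cost.** One extra table, a few sentences, and a sensitivity estimate that may look less favourable than the main one.

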## **6.7. Long Term Survival Follow-Up**

Phase 2 Dose Expansion subjects will participate in long term survival follow-up. These subjects will be contacted via phone call every 3 months for determination of long term survival status and record of any other anti-cancer therapy for up to 2 years after the last dose of IP. For subjects who discontinued the study for reasons other than disease progression, the Investigator should obtain information on the subject's post-study anti-cancer therapies, surgeries, and date of definitive disease progression (if known).

Subjects who are alive at the time the sponsor has made the determination the study will be ended will receive a final follow-up phone call to assess survival status and communicate the sponsor's decision. These subjects will be censored on the date the subject was last contacted.

The investigator will make every effort to contact the subject or a close relative or caretaker by phone to collect survival information. The investigator should show due diligence by documenting in the source documents steps taken to contact the subject i.e., dates of phone calls, registered letters, etc.

